3.2 Secondary Endpoints

The secondary endpoint is the occurrence of ischemic stroke or systemic embolism at 12 months from the time of implant.

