3.5 Endpoints Analysis Included in the Clinical Study Report

For the primary endpoint report (30-100 days post procedure), below endpoint assessments will be included:

- Primary effectiveness endpoint, which refers to the occurrence of non-effective LAA closure at first 30-100 days follow-up.
- Primary safety endpoint, which refers to the occurrence of the primary safety endpoint events between the time of implant and within 7 days following the procedure or by hospital discharge (whichever is later).
- Additional endpoints and other major clinical events, including the occurrence of below events at 30-100 days follow-up:
 - stroke, including ischemic and/or hemorrhagic
 - TIA
 - cardiovascular death, including cardiovascular and/or unexplained cause
 - systemic embolism
 - device embolization
 - device thrombus
 - serious pericardial effusion
 - major bleeding

For the 12-month report, below endpoint assessments will be included:

- Primary effectiveness endpoint, which refers to the occurrence of non-effective LAA closure at 30-100 days follow-up.
- Primary safety endpoint, which refers to the occurrence of the primary safety endpoint events between the time of implant and within 7 days following the procedure or by hospital discharge (whichever is later).
- Secondary endpoint, which refers to the occurrence of ischemic stroke or systemic embolism at 12-month follow-up.
- Additional endpoints and other major clinical events, including the occurrence of below events at 12-month follow-up:

Form/Template 90702621 Rev/Ver AF, Boston Scientific WATCHMAN FLX™ HK Study, SAP, 92820808, Rev/Ver AA Page 9 of 14

- stroke, including ischemic and/or hemorrhagic
- TIA
- cardiovascular death, including cardiovascular and/or unexplained cause
- systemic embolism
- device embolization
- device thrombus
- serious pericardial effusion
- major bleeding

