7.3 Clinical Event Rates

- 1. Rates at Procedure: the proportion of subjects who experience an event on the same day as the index procedure out of all subjects.
- 2. Rates through Discharge/7 days Post-procedure: the proportion of subjects who experience an event through discharge or 7 days post-procedure (whichever comes later) out of all subjects.
- 3. Rates at 30-100 Days Post procedure: the proportion of subjects who experience an event through 30-100 days post-procedure out of the subjects who have either had an event within 30-100 days post-procedure or who were event-free with last follow-up at least 30 days post-procedure.
- 4. Rates through 1-Year Post procedure: the proportion of subjects who experience an event through 365 days post-procedure out of the subjects who have either had an event within 395 days post-procedure or who were event-free with last followup at least 335 days post-procedure.

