7.5 Missing data

Missing data will not be dealt with systematically in this small sample size study. For the primary safety endpoint, all attempted subjects will be eligible for evaluation, regardless of implant success. Statistical models that account for censored data will be employed for time-to-event outcomes.

When calculating rates of adverse events, missing and partial dates will be handled as shown below:

| Partial Date Description | Action Taken |
|--|--|
| Entire onset date is missing | The procedure date will be used for the |
| | onset date. |
| The month and the day of the month are | January 1 st will be used for the month and |
| missing but the year is available | day of the onset date. However, if the |
| | imputed date falls before the procedure |
| | date, then the procedure date will be used |
| | for the onset date. |
| Day is missing, but the month and year are | The 1 st will be used as the day of the onset |
| available | date. However, if the imputed date falls |
| | before the procedure date, then the |
| | procedure date will be used for the onset |
| | date. |

Missing data for primary end point analysis will follow imputation techniques

Missing data due to dropped out or withdrawn subjects will be considered as missing at random and multiple imputation will be done based on the same assumption, while missing of the follow up data will be considered as missing not at random and imputation will follow the same techniques.

A tipping-point analysis might be conducted for the Primary Effectiveness Endpoint to assess the impact of different assumptions about the missing data on interpretation of the results.

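### The SAP's 1-year rate drops event-free subjects who die or leave before day 335 but keeps every subject with an early event, which slightly overstates the 12-month stroke/embolism risk

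*SAP*

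**What the plan says.** SAP 3.2 defines the endpoint: "The secondary endpoint is the occurrence of ischemic stroke or systemic embolism at 12 months from the time of implant". Death is not a component. SAP 3.5 words it for the 12-month report as "occurrence of ischemic stroke or systemic embolism at 12-month follow-up", and the SAP study summary puts that visit at 365 ± 30 days, which is day 335 to day 395.

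SAP 7.3 item 4 is the only rule that turns events into a 1-year rate.
- Numerator: "the proportion of subjects who experience an event through 365 days post-procedure".
- Denominator, first group: those "who have either had an event within 395 days post-procedure".
- Denominator, second group: those "event-free with last followup at least 335 days post-procedure".

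SAP 7.2 dates last follow-up by the End of Study form, which covers death, withdrawal, loss and completion. SAP 3.4 and 4.2 give a general censoring rule for time-to-event analyses, and SAP 7.5 adds: "Statistical models that account for censored data will be employed for time-to-event outcomes". None of these sections names an estimator or attaches one to the secondary endpoint. The imputation text in SAP 7.5 is confined to the primary endpoint, and the optional tipping-point analysis to primary effectiveness.

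**The concern.** Whether a subject counts in the denominator depends on that subject's outcome. Someone who has a stroke on day 60 and dies on day 90 is in both parts of the ratio. Someone who dies on day 90 without a stroke is in neither, although the risk of stroke was observed for 90 days. The rule therefore conditions on staying alive and in the study for about 11 months, but only for subjects without an event.

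This is the study's only secondary endpoint. In a descriptive study the reported rate and its interval are the result. Protocol section 6 and SAP section 2 say the data may support product registration elsewhere, by showing that ethnic difference might not matter to device performance. A rate that moves with deaths and dropout is a weaker basis for that comparison.

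**Working it through.** **Check on the plan's own figures.** The plan gives no expected 12-month rate, death rate or loss rate. Its one precision table (SAP 3.1) gives exact intervals for 0 to 5 events among 50. Clopper-Pearson limits reproduce all six rows; for example, 2/50 gives 0.5-13.7%.

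**Worked example (all counts assumed).** N = 40, which is the minimum SAP 4.1 expects in the primary analysis sets. There are 2 events by day 365, and 3 deaths and 2 losses before day 335, all without the event.
- SAP rule: 2/(40 − 3 − 2) = 2/35 = 5.7%, exact 95% CI 0.7-19.2%.
- Cumulative incidence (Aalen-Johansen, death competing), both events before any exit: 2/40 = 5.0%.
- Both events after all exits, losses before deaths: (1 − 3/38) × 2/35 = 5.3%. With deaths before losses: (37/40) × 2/35 = 5.3%.
- Difference: 0.4 to 0.7 percentage points.

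With 1 event the same exits give 1/35 = 2.9% against 2.5-2.6%. With 0 events every rule gives 0%.

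**Second example.** N = 50, 2 events, 5 early exits (an assumed 10%). The SAP rule gives 2/45 = 4.4%. An actuarial rate with half exposure for exits gives 2/47.5 = 4.2%. If all five exits are deaths, cumulative incidence is 2/50 = 4.0%.

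**In expectation.** Let the yearly event rate be λ and the yearly exit rate μ, both constant, with s = λ + μ and u = 335/365.
- Expected event fraction: E = (λ/s)(1 − e^(−s)).
- Expected event-free fraction retained: F = e^(−su) − (λ/s)(e^(−su) − e^(−s)).
- SAP ratio: E/(E + F). Kaplan-Meier target: 1 − e^(−λ). Cumulative incidence if every exit is a death: E.

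Take λ from 1.5% to 5% per year, the span of background ischemic stroke figures in Protocol 4.1 and 4.2. Assume μ from 5% to 20% per year. For λ = 2.3% (the CAP2 figure, read as yearly) and μ = 10%, the SAP ratio is 2.37%, the Kaplan-Meier target 2.27% and cumulative incidence 2.16%. Over the whole range the SAP ratio exceeds the Kaplan-Meier target by about 2-9% in relative terms. It exceeds cumulative incidence by about 5-20% if all exits are deaths.

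**Limits on the effect.**
- If there are no deaths and every loss precedes every event, the SAP ratio equals the cumulative incidence in that sample.
- Because SAP 7.2 uses the form date, a lost subject whose form is dated on or after day 335 stays in as event-free.
- An event-free subject last seen on days 335-364 counts as complete to day 365, which is a very small pull downward.

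**The 365/395 difference.** A subject with a first event on day 380 was event-free on day 365. For a 365-day risk that subject belongs in the denominator and not in the numerator, which is what item 4 does. If the endpoint means events up to the 12-month visit, the rule misses some. With 50 subjects, 2 events by day 365, 1 event on days 366-395 and no exits, it gives 2/50 = 4.0% instead of 3/50 = 6.0%. The expected number of such events among 50 is 50 × λ × 30/365, about 0.06 to 0.2.

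**The case against.** The strongest reply is that nothing turns on this rate. The study tests no hypothesis. The benchmark of up to 3 events is a count and applies only to the two primary endpoints. The error makes the device look worse. The example's exits are assumed, and a shift of 0.4-0.7 points is minor inside an interval of 0.7-19.2%. With 40 subjects and a 2.3% yearly rate, the chance of seeing no event at all is 0.977^40, about 39%. SAP 3.5 and 5.5 also report cardiovascular death and patient disposition, so many exits would be visible. All of this stands and limits the weight of the point, but it does not justify the denominator.

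Two stronger readings are tempting, and the documents do not support them.
- A reader might infer that the different day limits, "experience an event through 365 days post-procedure" above the line and "had an event within 395 days post-procedure" below it, bias the rate. They do not bias a 365-day risk. What remains is an unclear definition, because SAP 3.5 speaks of the 12-month follow-up.
- A reader might infer that SAP 7.5 sets up a second, conflicting estimator for this endpoint. Its sentence on censored data is limited to time-to-event outcomes, and no section assigns such an analysis to the secondary endpoint, which is worded as an occurrence at 12 months.

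One might also argue for Kaplan-Meier, or for a proportion with disclosed exclusions. That is partly a matter of preference with so few events. Cumulative incidence is the more direct answer because death is not part of the endpoint and prevents it from occurring.

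**Conclusion.** The point holds for the exclusion rule. Followed as written, SAP 7.3 item 4 overstates, in expectation, the 12-month risk of ischemic stroke or systemic embolism when subjects die or leave before day 335 without the event, and no other section supplies a different estimator for this endpoint. The size is 5.7% against 5.0-5.3% in the 40-subject example, which rests on assumed counts of events, deaths and losses. The bias is small beside the sampling error, runs against the device and enters no test. It is still worth correcting, because the remedy uses data already collected. The 365/395 wording needs a decision on what the endpoint means; it is not a second source of bias in a 365-day risk.

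**What to change.** - Report the secondary endpoint as the cumulative incidence of ischemic stroke or systemic embolism at day 365, with a 95% CI. Treat death without the event as a competing event and censor other early exits at last documented contact.
- If the crude rate is kept as support, state how many subjects it excludes and for what reasons.
- State whether the endpoint covers events through day 365 or up to the 12-month visit, whose window ends on day 395. If day 365 is kept, say that a subject with a first event on days 366-395 stays in the denominator as a non-event. Simply replacing 395 by 365 in the denominator could remove that fully observed subject and raise the rate.

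The cost is SAP wording and one standard procedure, with no new data.

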7.4 Calculation of age

The age will be calculated between the date of birth and the date of screening following this formula Age (in years) = (date of screening – date of birth) / 365. In case the day in the date of birth is reported as unknown (e.g. UN/05/1955), the value will be modified to 01 (e.g. 01/05/1955).

7.5 Missing data

Missing data will not be dealt with systematically in this small sample size study. For the primary safety endpoint, all attempted subjects will be eligible for evaluation, regardless of implant success. Statistical models that account for censored data will be employed for time-to-event outcomes.

When calculating rates of adverse events, missing and partial dates will be handled as shown below:

| Partial Date Description | Action Taken |
|--|--|
| Entire onset date is missing | The procedure date will be used for the |
| | onset date. |
| The month and the day of the month are | January 1 st will be used for the month and |
| missing but the year is available | day of the onset date. However, if the |
| | imputed date falls before the procedure |
| | date, then the procedure date will be used |
| | for the onset date. |
| Day is missing, but the month and year are | The 1 st will be used as the day of the onset |
| available | date. However, if the imputed date falls |
| | before the procedure date, then the |
| | procedure date will be used for the onset |
| | date. |

Missing data for primary end point analysis will follow imputation techniques

Missing data due to dropped out or withdrawn subjects will be considered as missing at random and multiple imputation will be done based on the same assumption, while missing of the follow up data will be considered as missing not at random and imputation will follow the same techniques.

A tipping-point analysis might be conducted for the Primary Effectiveness Endpoint to assess the impact of different assumptions about the missing data on interpretation of the results.

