A subject who signs informed consent, meets eligibility criteria and has had the WATCHMAN FLX Access Sheath inserted to implant the device, but eventually does not receive a WATCHMAN FLX device will be classified as "**Attempt**". These subjects may be withdrawn, unless a re-implant of a study device is planned, per physician discretion. If subjects are re-assessed for WATCHMAN FLX implant, as per physicians' discretion, then a reconsent must be obtained for participating in the registry. These subjects will be handled as "Implant" (see next section), if the re-implant is successful. Subjects who eventually have not received a WATCHMAN FLX device at the time of enrollment closure will remain classified as "Attempt" and be withdrawn. There are no FU requirements for Attempt subjects; however, adverse events will be collected up to the point of subject withdrawal. Attempt subjects count towards the enrollment ceiling and will be used for analyses of the endpoints. The original signed Informed Consent must be maintained in the center's study file and the following forms must be completed:

- eCRFs in the "Baseline" and "Implant" folders
- "Adverse Event" forms for any adverse event that occurs after signing the Informed Consent, up to the point of subject withdrawal.
- "Patient Status" form for withdrawal, when applicable.

The date at which the patient status form has been completed will be the point of subject withdrawal.

Implant

A subject who is successfully implanted with the WATCHMAN FLX device will be classified as "**Implant**". These subjects are followed in accordance with the FU schedule and included in all study analyses. All applicable case report forms per the protocol must be completed. The original signed Informed Consent and any relevant documentation must be maintained in the center's patient file.

Roll-in and non-roll-in

Each site might have up to 2 roll-in subjects if the site has never implanted a WATCHMAN FLX before. Roll-in subjects should be decided before the implant procedure, and might be classified as **Attempt** or **Implant** after the procedure. Roll-in subjects are enrolled and counted to the ceiling of the sample size. Other enrolled subjects are defined as non-roll-in.

Figure 2: Subject Status and Data Collection Flow Chart

11. Study Methods

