3 ENDPOINT ANALYSIS

3.1 Primary Endpoint

The Primary effective endpoint is the occurrence of non-effective LAA closure defined as any peri-device flow > 5mm demonstrated by TEE/CT/MRI at First Follow-up. The Primary safety endpoint is the occurrence of one of the following events between the time of implant and within 7 days following the procedure or by hospital discharge, whichever is later: all-cause death, ischemic stroke, systemic embolism, or device or procedure related events requiring open cardiac surgery or major endovascular intervention such as pseudoaneurysm repair, AV fistula repair, or other major endovascular repair. Percutaneous catheter drainage of pericardial effusions, snaring of an embolized device, thrombin injection to treat femoral pseudoaneurysm and nonsurgical treatments of access site complications are excluded from this endpoint.

No formal hypothesis will be tested for the primary endpoint. So, no formal sample size calculation is performed based on the primary endpoint. The following table provides a 95% confidence interval (exact methods) for a sample size of 50 if there are $0 \sim 5$ events.

| Events | Rates (n=50) | Lower 95%CI | Upper 95%CI |
|--------|--------------|-------------|-------------|
| 0 | 0% | 0.0% | 7.1% |
| 1 | 2% | 0.1% | 10.6% |
| 2 | 4% | 0.5% | 13.7% |
| 3 | 6% | 1.3% | 16.5% |
| 4 | 8% | 2.2% | 19.2% |
| 5 | 10% | 3.3% | 21.8% |

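### The onset-date rule in SAP 7.5 can turn an adverse event known to precede the procedure, or an undated event reported late, into a day-0 event

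*SAP*

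**What the plan says.** SAP 7.5 introduces its table of partial dates with the words "When calculating rates of adverse events, missing and partial dates will be handled as shown below". It makes no exception for the primary safety endpoint. The table has three rows:

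- Whole onset date missing: "The procedure date will be used for the" onset date.
- Month and day "missing but the year is available": 1 January of that year.
- Only the day missing: "The 1 st will be used as the day of the onset" date.

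In the second and third rows, a result earlier than the procedure is overridden ("date, then the procedure date will be used").

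The primary safety window in SAP 3.1 runs "between the time of implant and within 7 days following the procedure or by hospital discharge, whichever is later", so an event placed on the procedure date is inside it. SAP 7.3 defines a rate at procedure (same day), then rates through discharge or day 7, through 30-100 days and through one year.

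Pre-procedure adverse events can be in the database. Protocol 11.1 (Table 3) and 11.3 list adverse events among the data collected at the Enrollment Visit. For Attempt subjects, Protocol 10.3 also requires forms "for any adverse event that occurs after signing the Informed Consent, up to the point of subject withdrawal". At follow-up, Protocol 11.6 collects the events that occurred since the previous visit.

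**The concern.** The floor at the procedure date makes sense when the known part of the date leaves open whether the event came before or after the procedure. The table applies it even when the known month or year settles the matter. An event fully dated 20 May stays before a 15 June procedure. Lose the day, and the same event is counted on 15 June.

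The row for wholly missing dates has a related weakness. An event first collected at the 12-month visit as new since the last visit has a usable lower bound, but the table ignores it.

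The primary safety count, the rate at procedure and the 30-100 day rates are at stake. SAP 3.5 reports primary safety in both the 30-100 day and the 12-month report, so an undated qualifying event learned of late could change that count between reports. Protocol 6 and SAP 2 also say the data may be used to argue that ethnic difference matters little, and Protocol 6 names the U.S. study as the comparison. Events added by a date rule would blur that comparison.

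**Working it through.** **The plan's own figures.** The exact (Clopper-Pearson) intervals for 0 to 5 events in 50 in SAP 3.1 reproduce. For example, 0/50 has upper limit 1 − 0.025^(1/50) = 7.1%, and 3/50 gives 1.3% to 16.5%.

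**The rule as a formula.** Let P be the procedure date.
- Whole date missing: onset = P.
- Year only: onset = later of (1 January of that year, P).
- Day missing: onset = later of (1st of that month, P).

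**Known to be before the procedure.**
- P = 15 June 2021, onset May 2021: later of (1 May, 15 June) = 15 June, day 0.
- P = 10 January 2021, onset 2020: later of (1 January 2020, 10 January 2021) = 10 January 2021, day 0.

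Every onset with a known month or year before that of the procedure goes to day 0.

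**Known to be in a later month or year.** P = 15 June 2021, onset December 2021 gives 1 December, day 169. I ran all 365 procedure dates of 2021 against onsets on days 1 to 365. None of 127,852 combinations with a known later month, and none of 66,795 with a known later year, was set to the procedure date. About 2.0% and 3.8% still fell in days 0 to 7, because the first of the month or year came just after the procedure. For example, P = 28 December 2021 with onset 2022 gives 1 January, day 4.

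**True late events placed in days 0 to 7.** I assume onset uniform over days 8 to 365 and discharge by day 7. There are 365 × 358 = 130,670 combinations.
- Whole date missing: 100%.
- Year only: same-year onsets set to P number 357 × 358 / 2 = 63,903. Procedures on 25-31 December add 7 × 358 = 2,506. Total 66,409 / 130,670 = 50.8%.
- Day missing: onsets later in the procedure's own month number 3,154. Onsets in the next month, when its first falls within 7 days of P, number 2,219. Total 5,373 / 130,670 = 4.1%, with no true onset later than day 37.

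**Which rates change.** A pre-procedure event moved to day 0 enters every cumulative rate in SAP 7.3. A true day-200 event moved to day 0 wrongly enters the procedure, 7-day and 30-100 day rates, but it counts once in the one-year rate either way.

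**Size of one false primary safety event.** SAP 4.1 expects at least 40 subjects in the set (50 less up to 5 × 2 roll-ins).

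| Events | n = 40 | n = 50 |
|---|---|---|
| 0 | 0% (0 to 8.8%) | 0% (0 to 7.1%) |
| 1 | 2.5% (0.1 to 13.2%) | 2.0% (0.1 to 10.6%) |
| 3 | 7.5% (1.6 to 20.4%) | 6.0% (1.3 to 16.5%) |
| 4 | 10.0% (2.8 to 23.7%) | 8.0% (2.2 to 19.2%) |

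**The case against.** The strongest reply is that the rule is conservative: it can only raise the early safety rate, so it works against the device. For a wholly missing date with no other information, that is a fair worst-case choice, and this part of the objection stands. It does not cover the case where the recorded month or year rules the procedure date out. There the rule overrides information; it does not resolve doubt.

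A second reply is that a false primary safety event needs an unlikely chain, and this largely stands. The endpoint counts only death, ischemic stroke, systemic embolism, and device- or procedure-related events needing open cardiac surgery or major endovascular intervention. A subject who dies before the procedure is classed as Intent and is outside the analysis (Protocol 10.3). An event caused by the device or implant procedure cannot precede it. What remains on the pre-procedure route is essentially an ischemic stroke or systemic embolism between consent and implant, in a subject who still goes to procedure, with an incomplete date never resolved. Such an event would ordinarily be serious, and Protocol 20.1 sets 24-hour reporting for serious events. Data queries (Protocol 13.1) and monitoring (Protocol 17) should recover most dates. Non-serious events have 10 working days and the 12-month contact may be by phone, so incomplete dates are more plausible among them.

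A third reply concerns the remedy. Protocol 11.6 asks for events since the last visit but describes no positive record that an event was absent. A visit interval is therefore good evidence of a lower bound, not proof. That is a reason to keep the present rule as a sensitivity analysis.

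A reader might also infer that the table moves events known from their onset date to be long after the procedure, or that it corrupts every timed rate. The documents support neither. A known later month or year is kept, and the one-year rate still counts a late event once. Late onset is overridden only where it is known from other records (visit, report or end dates) and the onset date is wholly missing or gives only the procedure year.

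**Conclusion.** The rule is wrong as written in one respect and needlessly blunt in another. An event whose known month or year ended before the procedure is always counted on day 0. A wholly undated event, or one dated only to the procedure year, is also put on day 0 whatever the visit interval says. The early-window rates and event timing are affected; for pre-procedure events, so are the later cumulative rates.

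Severity is low to moderate. One false primary safety event would move 0/40 to 2.5% (0.1 to 13.2%), or 3/40 to 4/40 (7.5% to 10.0%), past the informal benchmark. That is the size of the error if it happens. The documents give no frequency of incomplete dates, and the safeguards above make it uncommon for endpoint components. The benchmark is not a decision rule, since no hypothesis is tested.

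The conclusion assumes that the table governs the primary safety endpoint. Its introductory sentence covers adverse event rates without exception, but SAP 7.5 also says that missing primary endpoint data will follow imputation techniques and does not relate the two.

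**What to change.** Amend the table in SAP 7.5 along these lines:

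1. Apply the procedure-date floor only when the known month or year is compatible with the procedure date. If it ends before the procedure, classify the event as pre-procedure and leave it out of the post-procedure rates.
2. When the date is wholly missing or year-only, use the earliest date compatible with the known part, the procedure date and the visit interval in which the event was reported, and no later than the report date or the event's end date. If these bounds conflict, query the site.
3. State whether this table governs the primary safety endpoint.
4. Keep the present rule as a worst-case sensitivity analysis for primary safety, and report how many events had an imputed date.

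A day-missing event in the procedure's own month remains ambiguous and would still go to the procedure date.

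The cost is a short SAP revision and slightly more date programming. The early safety rate also becomes less conservative than under the present rule, which the sensitivity analysis would show.
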